Subjects who are interested in participating based on review of printed or electronic recruitment materials will be directed to contact the Research Coordinator by phone, who will provide them with information about the study and the opportunity to ask questions about it in detail; those who express continued interest in participation will be screened for eligibility and ability to attend the scheduled classes, held at one of the five Fonseca Martial Arts dojos in Glenview, Wilmette, Park Ridge, Evanston, or Roscoe Village. Arm 1 will attend classes twice weekly for 6 months, with classes anticipated to run from January through June 2019. Afterwards, Arm 1 subjects may continue classes for a fee between July through December 2019 while subjects in Arm 2 crossover to the active portion and begin their six months of karate classes. Subjects can select from participating in either weekend/weekday daytime classes, or weekday/weekday evening classes, depending on their availability and proximity to each dojo's geographic location. Screening will occur on a rolling basis until the 52 participants are recruited.

Pre-Intervention Study Visit

All subjects will attend a pre-intervention study visit, at which time the study team, including Principal Investigator, Research Coordinator, and research assistants, will review the study design and flow, informed consent process, and each subject will be individually visited by a member of the study team to review and sign the informed consent form (ICF). No reconsenting will be necessary because Phase I participants will not be eligible to participate in Phase II, with the exception of participants who withdrew early from Phase I, who may enroll in Phase II provided that their reason for withdrawal no longer applies and these individuals will need to be newly consented with the Phase II consent document.

Subjects will complete a brief demographic and health questionnaire, including duration of PD diagnosis in years, current medication regimen, baseline activity level, prior involvement with karate or other martial arts, number of falls in the past 12 months, and subjects will complete the Parkinson's Disease Questionnaire-8 (PDQ-8)¹⁸, a brief, validated, PD-specific 8-item measure of quality of life. Subjects will complete the Hospital Anxiety and Depression Scale (HADS). Subjects will also write their response to the open-ended prompt, "What do you hope to achieve in this class?"

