Following six months of classes for Arm 1, and six months of usual exercise for Arm 2, the study team will contact subjects to schedule a six-month study visit, consisting of a repeated TUG, HADS, PDQ-8, SDMT, DST, MoCa, medication regimen and falls questionnaire, PAGEQ, PGIC, and MDS-UPDRS

examination. Each subject in Arm 1 will receive their initial response to the “What do you hope to achieve in this class?” prompt, and will be asked to reflect in a written, open-ended manner on whether they feel that they achieved their goal. Individuals in Arm 1 will be reminded that they may continue to attend karate classes, but the usual class fee per the dojo will no longer be waived. Individuals in Arm 2 will be informed that they may now begin karate classes at their dojo of choice for the following six months. This 6-month study visit is different than the 6-month follow-up call that was part of the initial KICK OUT PD pilot study; this six-month study visit is conducted in person, not by phone, and involves retesting of all of the measures from the initial, baseline visit. There will not be a 6-month follow up call in the new KICK OUT 2.

Twelve-month study visit

Following twelve months of classes for those individuals in Arm 1 opting to continue, and six months of classes for participants in Arm 2, the study team will contact subjects to schedule a twelve-month study visit, consisting of a repeated TUG, HADS, PDQ-8, SDMT, DST, MoCa medication regimen and falls questionnaire, PAGEQ, PGIC, and MDS-UPDRS examination. Each subject will receive their initial response to the “What do you hope to achieve in this class?” prompt, and will be asked to reflect in a written, open-ended manner on whether they feel that they achieved their goal. In addition, subjects will indicate their response to the following questions regarding feasibility: “Would you recommend this program to someone else with PD?” and “If available, would you continue to participate in this or a similar karate class?” Following completion of all assessments, all subjects will be asked to stay and participate in a brief focus group to reflect on the entire study. Given the number of subjects, study staff may divide the group into Arm 1 and Arm 2 participants, with concurrently running focus groups in separate rooms to ensure all participants have the opportunity to speak. The script for both groups will be identical.

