As noted above, due to the Covid-19 outbreak, remaining 12-month data assessments will be administered electronically for participants. Treatment, HADS, IPAQ, PDQ-8, Attendance and Camaraderie, Global Impression of Change, & Post-Intervention questionnaires will be administered over the phone and/or video call. UPDRS will be administered over video call. Cognitive test DST will be administered over the phone. Necessary visual components for the cognitive tests SDMT and MoCA will be emailed to participants to complete and return, and the remainder of these assessments will be administered over the phone. Study team will directly enter all data into REDCap.

Documentary

Portions of the karate classes and 12-month study visit, and potential in-depth interviews, will be videotaped by the Columbia filmmakers using personal equipment. Subjects may choose to not participate in the documentary project which means subjects will not participate in the in-depth video interviews, and they will not be included in individual or group video shots during the focus groups and karate classes.

Assessments: Subjects who agree to be part of the study and sign the Informed Consent Form will be asked to complete a series of assessments to determine their current neurological status and overall wellbeing. There is no known risk associated with participation in these assessments, and they are a part of routine clinical care for these conditions. These tests are typically experienced as interesting to subjects. Administration of these assessments may take up to 60 minutes per subject at the pre-intervention study visit, 6-month study visit, and 12-month study visit. Administration of the bimonthly

online survey assessments may take up to 20 minutes. All or some of the following assessments and self-report measures may be administered but are not limited to:

- *Demographic/disease questionnaire*: This brief, one-page questionnaire will ask for the subject's name, age, gender, race, ethnicity, PD duration in years, prior exposure to karate or martial arts classes, baseline activity level, and number of falls in the past 12 months. There will be one open-ended question asking, "What do you hope to achieve in this class?"

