Data will be exported from REDCap in de-identified format for statistical analysis, with all PHI stripped from the dataset prior to analysis by statisticians. We will summarize categorical variables by frequencies and percentages and will assess continuous variables for normality, summarized by mean/standard deviation, or median/interquartile range. We will report the basic descriptive statistics of the cohort, including baseline demographics, TUG, MDS-UPDRS, HADS, PDQ-8, IPAQ, SDMT, MoCa, and DST. We will report on attendance, defined as the percentage of classes attended, in each arm once active. We will analyze the change in TUG, MDS-UPDRS, HADS, PDQ-8, IPAQ, SDMT, DST, MoCa, and PAGEQ respectively, from baseline to six months, comparing Arm 1 and 2 (active vs. control), and again at twelve months to determine whether longer participation yields additional benefits, using paired *t*-tests or nonparametric Wilcoxon sign rank tests, as appropriate. We will report on the percentage of subjects endorsing each of the 7 PGIC response options at six and twelve months, between Arms, respectively. We will report the descriptive statistics concerning whether subjects’ individual predefined goal for the class was achieved (binary outcome), and will present de-identified qualitative comments noted in the feedback at the study visit focus groups. We will report descriptive statistics on continued interest and likelihood of recommending the program to someone else with PD. We will analyze descriptive statistics on continued involvement in karate/martial arts, and will again report the percentage of subjects endorsing each PGIC response option.

The qualitative data from the study visit focus groups will be audio-recorded and transcribed, with all identifying information stripped from the transcripts. Once transcribed, the audio recordings will be destroyed. The qualitative data will be analyzed using a grounded theory approach to identify pertinent themes, with data stored as password-protected files behind the Rush firewall, accessible only to study staff.

All video footage will be the sole property of the PI. Videos will have identifying information (i.e. image of patient’s face, first name). Video files will be stored and password-protected behind the Rush and the Columbia firewalls. The video along with the data collected from the focus groups and karate classes may be used as part of the dissemination of the study results and for educational purposes.

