Only the PI and research staff will have access to the database and hard copies of study documents. Data will be stored in a format suitable for research inquiries by the PI who might make use of the data in a retrospective manner for other Rush-based research studies. If a particular researcher/collaborator has an interest in a study population, then the PI will review the database to identify eligible subjects that meet the study inclusion criterion and the potential participant(s) will then be contacted by a member of this study team whom the subject has already met to see if they are interested in participating in the particular study. If a participant is interested, he or she will be referred to that Rush study team and will be scheduled for a separate consent procedure with the individual Rush researcher for that particular study and at that point the participant can choose whether to participate or not in that particular study. The results of the Karate for PD study may be published in a book, journal, and other media or used for teaching purposes. However, all published data will be made anonymous.

IV. Risk/Benefit Assessment

IV.a. Risk

There are no known risks from participating in neurological or neuropsychological tests. Subjects may experience mild boredom or cognitive fatigue; however, most individuals with like symptoms find the tests interesting and are able to tolerate up to two-hour duration of testing well. There is, however, a risk of falls or injury associated with participation in any exercise, including karate, for which subjects assume the risk and liability as they would with participation in any voluntary exercise activity. The risks will be minimized to the extent possible by 1) having all instructors undergo basic instruction in principles of PD by the PI prior to the first class; 2) having all classes held at quieter times in the dojo, so as to avoid overcrowding and risks of falls or freezing of gait in crowded, busy situations; 3) having small instructor to subject ratios to allow for maximal supervision and guidance; 4) having study staff available by phone to answer any questions or address concerns.

Another possible risk is the loss of confidentiality by participating in the documentary because the subject's image may be captured. However full names will not be used during interviews with the subjects who agree to answer questions about their experiences with the karate classes.

IV.b. Potential Benefit to Subjects

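### The follow-up falls window is not stated, the only falls item defined looks back 12 months, and no summary of falls or adverse events by arm is planned

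*Combined protocol and SAP*

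**What the plan says.** - **Baseline.** The Pre-Intervention Study Visit (III) collects "prior involvement with karate or other martial arts, number of falls in the past 12 months". The Assessments list defines the same item, "number of falls in the past 12 months", under the Demographic/disease questionnaire. No other falls item or recall period is defined in the document.
- **Follow-up.** The Six-month and Twelve-month study visit sections each list, among the repeated assessments, "medication regimen and falls questionnaire, PAGEQ, PGIC, and MDS-UPDRS", with no window. The first adds that the six-month visit "involves retesting of all of the measures from the initial, baseline visit". That visit is timed "Following six months of classes for Arm 1, and six months of usual exercise for Arm 2".
- **Harm and purpose.** IV.a states: "There is, however, a risk of falls or injury associated with participation in any exercise, including karate". I.c gives fall prevention as one purpose of the class content.
- **Analysis.** III.b says: "We will analyze the change in TUG, MDS-UPDRS, HADS, PDQ-8, IPAQ, SDMT, DST, MoCa, and PAGEQ respectively". This covers baseline to six months by arm, and again twelve months. Falls are not among these nine outcomes, nor among the measures named for the baseline description. Adverse events have no planned summary; III.b only sends them to the principal investigator for review as each occurs.
- **Other collection.** The bimonthly online survey has no falls item. The Covid-19 lists for remote month-12 assessment (I.c and III, Twelve-month study visit) do not name the falls questionnaire.

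**The concern.** The first six months are the only period in which karate and usual exercise are compared by randomisation. After that, Arm 2 also attends karate and Arm 1 may continue at its own cost. A falls question asked at month 6 is useful for comparing arms if it covers those six months. The only window on paper covers twelve.

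The second part does not depend on the window. Falls are the physical risk the protocol names for the classes and also something the classes aim to prevent, yet the plan has no table that sets the arms side by side. The trial could report better mobility with no planned comparison of falls, injuries or adverse events. For a harm, a ratio pulled toward 1 by pre-randomisation falls would be falsely reassuring.

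**Working it through.** The documents give no falls rate and no design figure for falls, so there is nothing of the plan's own to reproduce. The rates and rate ratios below are assumptions, shown over a range.

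**Inputs from the protocol.** Recall window 12 months (Assessments). Randomised follow-up at the second visit 6 months (Six-month study visit). Completers 40 in total, so 20 per arm (II.a).

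**Step 1: what a reused 12-month item would cover.**
- Month 6, both arms: 12 − 6 = 6 months before randomisation, or 6/12 = 50% of the window.
- Month 12, Arm 2: 6 months of usual exercise plus 6 months of karate in one count.
- Months 0-6 fall inside both the month-6 and the month-12 answers.

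**Step 2: ratio scale at month 6.** Let the monthly rate be r in both arms before randomisation and in Arm 2 afterwards, and r × RR in Arm 1 afterwards.

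Observed ratio = (6r + 6r·RR) / 12r = (1 + RR)/2. Share of Arm 1's reported falls that precede randomisation = 6r / (6r + 6r·RR) = 1/(1 + RR).

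| True RR | Observed, 12-month window | Arm 1 falls before randomisation |
|---|---|---|
| 0.5 | 0.75 | 67% |
| 1.5 | 1.25 | 40% |
| 2.0 | 1.5 | 33% |
| 3.0 | 2.0 | 25% |

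With a window that starts at randomisation, the observed ratio equals the true one.

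**Step 3: difference scale at month 6.**
- 12-month window: (6r + 6r·RR) − 12r = 6r(RR − 1).
- 6-month window: 6r·RR − 6r = 6r(RR − 1).

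The expected difference in counts is the same, but the noise is not. Take Poisson counts, 20 per arm, 1 fall per person-year and RR = 2. The mean difference is 0.5 falls either way. Its standard error is √((0.5 + 1.0)/20) = √0.075 = 0.27 with six months and √((1.0 + 1.5)/20) = √0.125 = 0.35 with twelve. The ratio is √(0.125/0.075) = 1.29, a 29% larger standard error.

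**Step 4: consequence for a log rate ratio test.** Power = Φ(|ln(m1/m0)| / √(1/(20·m0) + 1/(20·m1)) − 1.96), where m0 and m1 are the mean counts per person in the window (two-sided 5%, RR = 2).

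| Assumed background rate | 6-month window | 12-month window |
|---|---|---|
| 1 per person-year | m0 = 0.5, m1 = 1.0: 0.43 | m0 = 1.0, m1 = 1.5: 0.29 |
| 2 per person-year | m0 = 1.0, m1 = 2.0: 0.72 | m0 = 2.0, m1 = 3.0: 0.51 |

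With overdispersion (1/m replaced by 1/m + 1 in each arm) these fall to 0.28 versus 0.16, and 0.38 versus 0.19. The comparison is imprecise under either window, and more so under the longer one.

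**Step 5: the analysis list.** Set beside each other, IV.a names falls or injury as a risk, the visit sections collect falls twice after baseline, and III.b uses those answers nowhere. No arithmetic is needed here.

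**The case against.** **The follow-up window is inferred.** The 12-month wording sits in an intake form that also asks for name, race and prior martial arts. The follow-up item has a different title, the Assessments list allows other instruments, and the form itself is not in the documents. The sentence about retesting all measures mainly distinguishes the visit from the pilot's phone call, and the re-administered list in I.c does not name falls. A reader might conclude that the trial does use a 12-month window at month 6. The documents do not establish that; they show only that no other window is given. This part of the objection stands, and Steps 1 to 4 are conditional on reuse of the baseline item.

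**The effect is not simply halved.** A reader might infer that any harm or benefit is cut in half. Only the excess of the rate ratio over 1 is halved. Randomisation balances earlier falls in expectation, so the count difference keeps its size and loses precision (Step 3). This also stands.

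**Falls are not a declared outcome.** They appear in neither the hypotheses nor the exploratory outcomes, and III.b classes the study as minimal risk. Calling them the trial's main safety outcome would go beyond the text, which says only that exercise carries "a risk of falls or injury associated with participation in any exercise, including karate".

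**Adverse events are already reviewed.** That is so, and a reader should not infer that safety goes unmonitored. But III.b does not define a fall as an adverse event, say how events are elicited, or plan a summary by arm. In months 0-6 Arm 1 meets instructors twice a week and Arm 2 does not, so unprompted reports could differ between arms. Review as events occur does not replace a question asked identically in both.

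**The yield is small.** Step 4 agrees, which is a reason to label the estimate descriptive. It is not a reason to leave out the table.

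**Conclusion.** The point holds in two parts of different strength.

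1. Certain on the text: no summary of falls or adverse events by arm is planned, although falls or injury is a risk the protocol names and falls are asked about at follow-up.
2. Conditional: the follow-up window is unstated. If the baseline item is reused, half of the month-6 window precedes randomisation and Arm 2's month-12 window mixes the two conditions. The observed rate ratio is then (1 + RR)/2, for example 1.5 for a true 2.0. That figure assumes equal and constant background rates. The expected count difference is not biased; in the illustration its standard error rises by 29%.

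The change should be made because it is cheap and gives a cleaner comparison of a named harm. It does not affect the TUG analysis or the sample size.

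**What to change.** - State the follow-up falls window as since your last study visit, in identical words for both arms at months 6 and 12. Keep the 12-month item at baseline.
- Name the falls item in the Covid-19 remote month-12 list. If the form listed there as Treatment already carries it, say so.
- Add to III.b a table of falls, fallers, injuries and adverse events by arm and period, with person-time. Months 0-6 are the randomised comparison. Give a falls rate ratio with 95% CI, baseline 12-month falls as covariate, labelled descriptive.
- A falls item in the bimonthly survey, for both arms, is optional.
- If six-month visits are already complete, state the window that was used. If it was 12 months, report the difference in counts between arms and do not present the ratio as the effect over months 0-6.

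**Cost.** One wording change, one line in the remote list and one table. The estimate will be imprecise with about 20 completers per arm and cannot support a claim of safety or of fall prevention.

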After the training, eligible subjects will be grouped by dojo preference, and randomized 1:1 within each dojo into **Arm 1**: immediate participation in six months of twice-weekly karate classes, or **Arm 2**: usual exercise for six months. After six months, Arm 1 participants may opt to pay for dojo membership and continue classes, and Arm 2 participants will crossover and begin six months of twice-weekly karate classes. Only the Research Coordinator will know which subjects belong to Arm 1 and Arm 2, and she/he will deliver all study-related communication to the subjects.

The karate classes have been specifically designed for individuals with early- to middle-stage PD, focused on incorporating upper and lower limb movements in multiple directions, increasing awareness throughout the body, shifting body weight and rotation, relaxation of the muscles, improving reaction time, using complex repetitive actions to improve coordination, footwork training and centered weight shifts to help with fall prevention, and striking shields for self-defense and stress relief. The PI and study team will provide instruction on PD to all instructors prior to study launch, and will be available and responsive to any questions or concerns throughout the course of the study. The structure of the 6-

month curriculum will be identical at each of the five dojo locations. If a subject misses a class, they may choose to make up a class at one of the other dojo locations.

Every two months, subjects in both Arms will receive an online link to report their attendance at classes, indicate whether their PD medication regimen has changed (as a potential confounder), and complete the IPAQ, HADS, and PDQ-8. In addition, the survey will contain the Physical Activity Group Environment Questionnaire (PAGEQ) to measure camaraderie, and Patient Global Impression of Change (PGIC) for the subject's global impression of change. The online survey will be delivered through a secure online database called Research Electronic Data Capture (REDCap). The purpose of the online surveys is to track adherence to karate classes, adherence to other walking/moderate/vigorous activity, quality of life, anxiety, depression, global impression of change, and group cohesion.

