After six months, participants in both arms will have a second in-person study visit in which the pre-intervention assessments will be re-administered (MDS-UPDRS, TUG, IPAQ, MoCA, PDQ-8, HADS, SDMT, DST, and instrumented gait analysis), along with the PAGEQ and PGIC. The PI and co-investigators performing the MDS-UPDRS will be blinded to subjects' assignments. Following completion of all assessments, without the blinded raters present, all participants will be reminded to continue completing the bimonthly online surveys over the upcoming six months, and the Research Coordinator will explain to Arm 2 on the crossing over process into the active intervention (karate classes), and participants will be provided with information on the timing and location of classes. Individuals in Arm 1 will be asked to stay and participate in a brief focus group on the first six months of classes; PI and co-investigators will not be present during the focus group in order to preserve the blind. Subjects will be prompted to share their thoughts on how the intervention impacted their overall wellbeing, balance, and mindfulness; whether the intervention achieved their expectations; whether they intend to continue, and what feedback they would like to provide.

After twelve months, participants in both arms will have a third in-person study visit* in which the pre-intervention assessments will be re-administered (medication regimen, MDS-UPDRS, TUG, IPAQ, MoCA, PDQ-8, HADS, SDMT, DST, and instrumented gait analysis), along with the PAGEQ and PGIC. The PI and co-investigators performing the MDS-UPDRS will remain blinded to subjects' assignments. Following completion of all assessments, all subjects will be asked to stay and participate in a brief focus group to reflect on the entire study. Given the number of subjects, study staff may divide the group into Arm 1 and Arm 2 participants, with concurrently running focus groups in separate rooms to ensure all participants have the opportunity to speak; again, PI and co-investigators performing ratings will not be present to preserve blinding. The script for both groups will be identical.

*Covid-19 Procedures for 12 month study visits:

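### PAGEQ change from baseline is planned but no baseline PAGEQ is scheduled, and Hypothesis 2 on PGIC is a one-group statement under a comparative aim

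*Combined protocol and SAP*

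**What the plan says.** **PAGEQ.** The opening aims name camaraderie among the patient-reported outcomes to be compared with a standard exercise prescription, and the exploratory outcomes include change in group cohesion on the PAGEQ. Section III.b plans: "We will analyze the change in TUG, MDS-UPDRS, HADS, PDQ-8, IPAQ, SDMT, DST, MoCa, and PAGEQ respectively, from baseline to six months", Arm 1 against Arm 2, with a further analysis at twelve months. The same section lists the baseline descriptives as "baseline demographics, TUG, MDS-UPDRS, HADS, PDQ-8, IPAQ, SDMT, MoCa, and DST".

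The schedule is in I.c and III. Neither account of the baseline visit (I.c; III, Pre-Intervention Study Visit) includes PAGEQ. Section I.c introduces it with the two-monthly online survey: "In addition, the survey will contain the Physical Activity Group Environment Questionnaire (PAGEQ) to measure camaraderie". At the later visits I.c gives the re-administered pre-intervention tests in parentheses and then adds PAGEQ and PGIC: "MoCA, PDQ-8, HADS, SDMT, DST, and instrumented gait analysis), along with the PAGEQ and PGIC". Until crossover, Arm 2 is assigned to "usual exercise for six months".

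**PGIC.** Hypothesis 2 predicts that most subjects will be at least minimally improved after six months of classes. It names no comparator, although the aim for overall wellbeing is comparative. Section III.b will report the percentage in each of the seven categories by arm at six and twelve months. It plans no between-arm difference, interval or test.

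**The concern.** A change score needs two values. If PAGEQ was first given about two months after randomization, the planned baseline-to-six-month comparison has no starting point. The month-2 score cannot stand in for one, because Arm 1 has by then had about a third of its classes.

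The Arm 2 score has a second difficulty. PAGEQ rates the cohesion of a group, and Arm 2 has no study class before month 6. Without a defined reference group, it is unclear what its month-6 score measures.

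For PGIC, Hypothesis 2 could be called met whatever Arm 2 reports. Improvement on a global self-rating can reflect expectation, the exercise training given to everyone, or attention from the study. The randomized control arm would separate these from karate itself, but the hypothesis does not use it.

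**Working it through.** **1. Is there a baseline PAGEQ?**

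- *Against.* Both baseline descriptions omit it. Section I.c places it outside the re-administered baseline set. The baseline descriptives in III.b include IPAQ but not PAGEQ.
- *Apparently for.* The six-month visit (III) is described as "consisting of a repeated TUG, HADS, PDQ-8, SDMT, DST, MoCa, medication regimen and falls questionnaire, PAGEQ, PGIC, and MDS-UPDRS", and the text adds that it "involves retesting of all of the measures from the initial, baseline visit". But that list also contains PGIC, which cannot be a baseline measure, so the word for repetition does not govern every item. The second phrase does not say that PAGEQ was among the baseline measures.
- *Neutral.* The instrument list under Assessments opens with "All or some of the following assessments and self-report measures may be administered but are not limited to". It is permissive and gives PAGEQ no time point.

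The first scheduled PAGEQ is therefore the month-2 survey. Classes by then: 2 × 26 weeks = 52 over six months; 52/3 ≈ 17.

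**2. What PAGEQ can still show**

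Section II.a expects 40 completers, so 20 per arm. For a month-6 difference with equal SDs, the 95% CI half-width in SD units is t(0.975, n1+n2−2) × √(1/n1 + 1/n2), with n1 = 20. The number of Arm 2 completers with a group to rate is not given, so a range is assumed:

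| Arm 2 with a group (assumed) | t | √(1/20 + 1/n2) | Half-width (SD) |
|---|---|---|---|
| 20 | 2.024 | 0.316 | 0.64 |
| 15 | 2.035 | 0.342 | 0.69 |
| 10 | 2.048 | 0.387 | 0.79 |
| 5 | 2.069 | 0.500 | 1.03 |

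PAGEQ is also scheduled at months 6 and 12 in both arms, so a within-person 6-to-12 change is available. In Arm 2 it spans the crossover.

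**3. How easily can a PGIC majority arise without a karate effect?**

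The plan gives no expected rate, so the improvement rate p is assumed and is the same with or without karate. The hypothesis can be read for Arm 1 at month 6 (20 completers) or for both arms pooled after their own six months of classes (40 completers). The exact binomial chances of more than half are P(X ≥ 11 | 20, p) and P(X ≥ 21 | 40, p):

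| p (assumed) | 20%| 30% | 40% | 50% | 60% | 70% |
|---|---|---|---|---|---|---|
| Arm 1, n = 20 | <0.1% | 2% | 13% | 41% | 76% | 95% |
| Pooled, n = 40 | <0.1% | 0.2% | 7% | 44% | 87% | 99% |

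**4. What a between-arm PGIC estimate would show**

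- Precision with 20 per arm and p = 0.5 in both: 1.96 × √(2 × 0.25/20) = 0.31, or about ±31 points.
- Example, 11/20 against 8/20. Wilson limits are 0.342 to 0.742 and 0.219 to 0.613. The Newcombe lower limit is 0.15 − √[(0.55 − 0.342)² + (0.613 − 0.40)²] = −0.15. The upper limit is 0.15 + √[(0.742 − 0.55)² + (0.40 − 0.219)²] = 0.41.
- By the same method, 11/20 against 11/20 gives 0 (−28 to +28 points).

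On the Arm 1 reading, both examples satisfy Hypothesis 2, and neither shows an effect of karate.

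**The case against.** **The absence of a baseline PAGEQ is inferred from omission.** The baseline lists are not exhaustive: the procedures section leaves out IPAQ, which I.c includes. The instrument list is open-ended, III.b presupposes a baseline value, and the text available has no schedule-of-assessments table. This stands as a limit. A reader might infer that no baseline PAGEQ was collected; the documents show only that none is scheduled.

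**PAGEQ change is not lost altogether.** A reader might conclude that no completer can have a PAGEQ change score. That is too strong. Months 6 and 12 are scheduled in both arms, and the Covid-19 text keeps a camaraderie questionnaire. The twelve-month analysis could even be read as a 6-to-12 change.

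**Arm 2 may have a group to rate.** It is tempting to say that its month-6 score is meaningless. But usual exercise can be group exercise, and II.f excludes only recent karate, other martial arts or boxing programs. The score is undefined, not empty.

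**The PGIC gap is narrow.** PGIC is reported by arm, a difference can be derived from that table, and III.b does not plan to test or declare a majority. Hypothesis 1 is also worded within group, with III.b supplying the comparison. This largely stands: the control data are not ignored. But for Hypothesis 1, III.b compares change between arms; for PGIC it stops at percentages.

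**The chance of a spurious majority depends on the assumed rate.** It is negligible at 20% and near certain at 70%. No single figure should be quoted.

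**Conclusion.** The point holds in limited form.

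As scheduled, PAGEQ change from baseline is not computable at six or twelve months, so one listed exploratory analysis cannot be run as written. This rests on the available text and would change if a baseline PAGEQ was in fact collected. The undefined Arm 2 reference group would remain a gap even then.

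Hypothesis 2 cannot by itself support a claim that karate improves wellbeing relative to usual exercise, because it can be met with no karate effect. How often depends on a response rate that the plan does not give and on whether one arm or both are counted. The planned table by arm would reveal an equal response in Arm 2, but the hypothesis does not refer to it.

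Severity is low to moderate. PAGEQ is exploratory, the PGIC gap can be closed from data already scheduled, and nothing here affects the primary TUG analysis.

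**What to change.** **PAGEQ**

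1. Confirm whether a baseline PAGEQ was collected. If it was, document when and which group was rated.
2. If it was not, remove PAGEQ from the baseline-change list at both time points. Report the month-6 score by arm as an exploratory two-sample difference with 95% CI.
3. State which group Arm 2 rated and how many had one. If some had none, say that the comparison covers only those with a group and is no longer fully randomized.
4. Describe PAGEQ during karate: Arm 1 in months 2 to 6, Arm 2 in months 8 to 12, and Arm 1 continuers separately. Include the month 6-to-12 change, noting that for Arm 2 it spans the crossover.

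**PGIC**

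1. Add the six-month between-arm difference in the proportion at least minimally improved, with 95% CI, beside the seven-category table. Make it the basis for any claim about karate's effect on wellbeing.
2. Label any after-karate majority as uncontrolled, and say whether it counts Arm 1 or both arms.
3. Reconcile the two descriptions of PGIC (change from baseline in Hypothesis 2; response to the intervention under Assessments), or report the wording used.

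**Cost.** Only analysis and reporting text changes; no visit or data item is added. The Covid-19 wording about remaining twelve-month assessments suggests that six-month data are already in hand. Changes made after six-month data collection must be labelled post hoc and carry less weight. Both contrasts are imprecise. Against 8/20 in Arm 2, 14/20 in Arm 1 gives +30 points (−1 to +54) and 15/20 gives +35 (+4 to +58), so 15/20 is needed to exclude zero. Self-report is unblinded, and the Arm 2 rating group may be unrecoverable if the survey did not ask.
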